#### 11.3.2 Stool Frequency/Consistency

The mean derived weekly stool frequencies, mean changes from baseline, and mean percent changes from baseline will be summarized by IBS subtype, treatment group, and week. No summary will be done with the combined subtypes. No statistical inferences will be made.

Percent change will be calculated as follows:

- If baseline value is 0, change from baseline \* 100
- Otherwise, change from baseline/baseline result \* 100

The number of CSMBs will be summarized by week including the changes from baseline. Since these quantities are not expected to follow a normal distribution, the median changes from baseline and median percent changes from baseline will be compared using the Mann-Whitney test.

The percentage of days each week with at least one stool with a consistency of 6 or 7 will be summarized for IBS-C and a consistency of 1 or 2 will be summarized for IBS-D using the Bristol Stool Chart.

The derived data will be listed by evaluable week.

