5.1 Inclusion Criteria

All subjects must meet all the following inclusion criteria:

- 1. Written consent on an Institutional Review Board (IRB)/ Independent Ethics Committee (IEC) approved ICF before any study specific evaluation
- 2. Males and Females between 18 and 70 years of age
- 3. Body Mass Index (BMI): 18-39 kg/m²
- 4. Having IBS-C or IBS-D as defined by Rome IV, including Subtype Classification as defined per Table 2

Recurrent abdominal pain on average, at least 1 day/week in the last 3 months associated with two or more of the following criteria:

• Related to defecation

- Associated with a change in frequency of stool
- Associated with a change in form (appearance) of stool

The above criteria must be met for the last 3 months with symptom onset at least 6 months prior to diagnosis.

IBS-C and IBS-D subtypes will be further classified as follows:

Table 3:

IBS-C	IBS-D
□ Abdominal Pain Intensity: weekly average of worst daily (in past 24 hours) abdominal pain score of > 3.0 on a 0 to 10-point scale	\Box Abdominal Pain Intensity: weekly average of worst daily (in past 24 hours) abdominal pain score of > 3.0 on a 0 to 10-point scale
	And
And	
□ Stool Frequency: more than 25% of bowel movements with a consistency of Type 1 or Type 2 Bristol stool chart and less than 25% of bowel movements with Bristol stool form Type 6 or Type 7. Subject must have fewer than 3 CSBMs ¹ within a one week period (7 days)	□ Stool Consistency: more than 25% of bowel movements with a consistency of Type 6 or Type 7 Bristol stool chart and less than 25% of bowel movements with Bristol stool form Type 1 or Type 2. Subjects must have at least one Type 6 or Type 7 bowel movements on at least four days within a one week period (7 days).

*Stool types based on Bristol Stool Chart; Hard stools -Type 1 and 2; Soft stools – Type 6 and 7 (see Appendix 3). Source: (https://irritablebowelsyndrome.net/clinical/new-rome-iv-diagnostic-criteria/) (see Appendix 6) ¹ CSBM defined as a bowel movement that is both complete and spontaneous. Bowel movements where laxative use is recorded in the concomitant medication questions in a 24 hour period, by IBS-C subjects will not be counted as CSBMs when subtyping for randomisation.

- Have a moderate or severe IBS symptom severity score ; ≥175 at the screening visit as defined by IBS-SSS. A tolerance of -10% (≥ an IBS-SSS score of 157.5) will be allowable at the Baseline (Visit 1).
- 5.2 Exclusion Criteria

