Subjects will be asked to complete a quality of life questionnaire consisting of 34 questions with a five-point response. The individual responses to the 34 items are summed and averaged for a total score and then transformed to a 0-100 scale for ease of interpretation with higher scores indicating better IBS specific quality of life. Once subjects are randomised they will be asked to record their score on their smartphone at each clinic visit or within 24hrs prior to the Clinic Visit.

Hospital Anxiety and Depression Score (HADS) (Appendix 2)

Subjects will be asked to complete HADS which is a 14-item scale that generates ordinal data. Seven of the items relate to anxiety and 7 relate to depression. Each item is scored from 0-3 so a subject can score 0 to 21 for either anxiety or depression. Once subjects are randomised they will be asked to complete this questionnaire on their smartphone at each clinic visit or within 24hrs prior to the Clinic Visit.

Bristol Stool Chart

Subjects will be asked to record stool frequency and consistency. Stool types will be based on the Bristol Stool Chart (Appendix 3). This data will be recorded daily for a 7-day period up to Baseline (Visit 1) to allow Subject to be classified into Cohorts of IBS sub-types. Once subjects are randomised they will be asked to record their stool frequency daily up to 10 bowel movements per day and score each stool type on their smartphone. No bowel movements in any given day will also be recorded.

Stool frequency will be defined as a sum of weekly CSBMs. Stool frequency will be recorded using the following question: "How many times did you open your bowels during the past 24 hours? If you have not had any bowel movements today, please enter 0." Subjects will be reminded to rate all of their bowel movements in the Bristol Stool Chart before answering the question. CSBMs will be determined by absence of laxative use recorded in concomitant medication questions for the same 24 hour period.

IBS Symptom Severity Score (SSS) (Appendix 4)

Subjects will be asked to complete a questionnaire on severity of abdominal distension, severity of abdominal pain, frequency of abdominal pain, dissatisfaction with bowel habits, and interference of IBS symptoms with daily life. A score ranging from 0 (no symptoms) to 500 (maximum severity) can be achieved as mild (74-174), moderate (175-299) or severe (>300) IBS symptoms.

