The denominators for the weekly average of Abdominal Pain Intensity, the stool frequency, and the proportion of days per week with at least one Type 6 or 7 will be the number of days with an assessment during the week. The stool frequency will be multiplied by 7 to convert to a stools per week figure. The stool consistency will be multiplied by 100 to convert to a percentage.

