### 10.2 Baseline Values for Efficacy Assessments

For the daily assessments collected on the eCOA device, baseline values will be derived from the 7 consecutive days assessed preceding the Baseline (Day 1) visit used to assess eligibility. The baseline value will be considered missing if less than 4 of the 7 days have an assessment.

- Abdominal Pain Intensity (1-10)

- Stool Consistency (day with at least one bowel movement Type 6 or 7)
- Stool Frequency

The baseline value for each of these assessments will be calculated by summing the daily result over the 7-day period and dividing by the number of days with an assessment. The Stool Consistency baseline proportions will be multiplied by 100 to convert to a percentage.

Baseline for the other efficacy assessments is defined as the last non-missing value recorded on or before the Baseline (Day 1) visit.

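### The zero-baseline rule for percent change in CSBMs treats zero as one unit, and the SAP does not put baseline and follow-up stool frequency in the same unit

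*SAP*

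**What the plan says.** SAP 11.3.2 covers stool frequency and consistency, a listed secondary endpoint. It first summarises weekly stool frequency and its changes, without inference. It then defines percent change in two lines, each multiplied by 100: "If baseline value is 0, change from baseline" and "Otherwise, change from baseline/baseline result". The next paragraph turns to the weekly number of CSBMs and says that "the median changes from baseline and median percent changes from baseline will be compared using the Mann-Whitney test". The SAP gives no other percent-change formula for stool or CSBM data.

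SAP section 6 makes tests of non-primary efficacy endpoints two-sided at 0.05 unless stated otherwise. Sections 11.3.3 to 11.3.5 label their t-tests as exploratory; 11.3.2 puts no such label on the Mann-Whitney test.

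On units, SAP 10.1.1 says: "The stool frequency will be multiplied by 7 to convert to a stools per week figure". SAP 10.2 has the baseline "calculated by summing the daily result over the 7-day period and dividing by the number of days with an assessment", and the only conversion it adds concerns consistency: "The Stool Consistency baseline proportions will be multiplied by 100 to convert to a percentage". Protocol 7.1 says: "Stool frequency will be defined as a sum of weekly CSBMs".

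On entry to the IBS-C cohort, Protocol 5.1 says: "Subject must have fewer than 3 CSBMs" in the seven-day period, which is also the baseline window.

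**The concern.** Percent change from zero is undefined, and the SAP fills the gap by dividing by one. The ordinary formula is free of units, but the zero rule is not: its value is one size if frequency is counted per week and a seventh of that if it is counted per day. A rank test across both kinds of subject therefore depends partly on a choice that has nothing to do with treatment. A consistently stated unit would at least settle that choice in advance. Here the baseline and the follow-up values are described in different units, which also affects subjects whose baseline is not zero. At stake is a pre-specified secondary test in IBS-C whose p-value could turn on how a programmer resolves the text.

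**Working it through.** **The plan's own figure.** The documents give no power or expected result for the CSBM percent-change test. The only stated power is for the primary endpoint: at least 80% with 125 per arm, 40% v 55%, one-sided alpha 10%, Yates's correction. Exact binomial enumeration gives 82.5%, so that figure holds. Only the 125 per arm is carried forward.

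**Step 1: the formulas.** Let b and f be baseline and follow-up CSBMs per week.
- Both per week: 100f if b = 0; 100(f - b)/b otherwise.
- Both per day: 100f/7 if b = 0; 100(f - b)/b otherwise.
- Literal text (baseline per day from 10.2, follow-up per week from 10.1.1): 100f if b = 0; 100(f - b/7)/(b/7) = 100(7f/b - 1) otherwise.

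**Step 2: worked subjects.**

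| CSBMs per week | Both per week | Both per day | Literal mix |
|---|---|---|---|
| 0 to 2 | 200% | 28.6% | 200% |
| 0 to 3 | 300% | 42.9% | 300% |
| 1 to 1 | 0% | 0% | 600% |
| 1 to 2 | 100% | 100% | 1300% |
| 2 to 3 | 50% | 50% | 950% |

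Per week, the subject going from 0 to 2 ranks above those going from 1 to 2 and from 2 to 3. Per day, the same subject ranks below both. In the literal mix a zero-baseline subject needs more than 6 CSBMs a week (100f > 600) to outrank someone unchanged at 1.

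**Step 3: absolute change under the literal mix.** An unchanged subject scores b - b/7: 1 - 1/7 = 0.86 at one CSBM per week and 2 - 2/7 = 1.71 at two. The second would even meet the primary stool component (an increase of at least 1 per week) with no change at all.

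**Step 4: how many zeros.** A fully recorded IBS-C baseline week can hold 0, 1 or 2 CSBMs. The split is not given. Assuming a Poisson count with mean m truncated below 3, P(0) = 1/(1 + m + m²/2):
- m = 0.5: 1/1.625 = 0.62
- m = 1.0: 1/2.5 = 0.40
- m = 1.5: 1/3.625 = 0.28

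**Step 5: effect on the test (illustrative).** All simulations use 125 per arm and two-sided 0.05.
- Model A: baseline mean 1 as in step 4; follow-up Poisson with mean 2.0 + 0.6b on placebo and 2.6 + 0.6b on active; 4,000 trials. Power is 70% per week, 54% per day and 76% for absolute change.
- Model B: a fixed share of zeros, the rest split evenly between 1 and 2; follow-up Poisson with mean 0.9 + 0.9b, plus 0.4 on active; 2,000 trials per row.

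| Share of zeros | Power per week | Power per day | Significance verdict differs |
|---|---|---|---|
| 10% | 50.7% | 45.3% | 9% |
| 25% | 55.9% | 44.9% | 17% |
| 40% | 60.7% | 45.7% | 22% |
| 60% | 69.3% | 55.8% | 20% |

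With no zeros the two units give identical p-values. With no treatment effect and 10-60% zeros, rejection stays near 5% in both units, though the verdict still differs in 3-4% of trials. The absolute-change p-value is the same in both units in every simulated trial.

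**The case against.** The strongest reply is that the documents point to weekly values throughout. SAP 10.1.1 converts to per week, 11.3.2 speaks of weekly frequencies, Protocol 7.1 defines a weekly sum, and the primary IBS-C component makes sense only against a weekly baseline. On that reading the unit is settled and the 54% power does not apply. This largely stands: nothing in the text puts follow-up on a daily scale, so the comparison of per day with per week shows how sensitive the rule is, not a choice the SAP offers. What remains is that 10.2 still lacks the factor of 7, and that a zero baseline is still scored as though it were 1 CSBM per week.

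It can also be said that the percent-change formula sits under a summary without inference, and that the table specifications (SAP Appendix C) are a separate document not available here. Applying the formula to the Mann-Whitney test is therefore an inference, but no other definition is offered.

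Finally, the consequence is limited. This is one secondary comparison, and absolute change is already tested in the same sentence.

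**Conclusion.** The point holds as a minor defect with a cheap remedy. The zero-baseline rule makes the position of zero-baseline subjects relative to the others depend on an arbitrary unit. Separately, the SAP describes baseline per day and follow-up per week; read literally, that gives +600% to an unchanged subject and distorts absolute change as well.

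Several stronger readings are tempting but not supported:
- **Zero baselines will be common.** The documents give only the entry range; 28-62% rests on the assumed Poisson model.
- **Only zero-baseline subjects are affected.** This is true when everything is rescaled together, but the one mismatch actually in the text distorts the non-zero baselines and leaves the zero ones alone.
- **The ranks are arbitrary throughout.** Order within the zero-baseline group is preserved.
- **False positives increase.** Type I error stays near 5% in either unit.
- **The primary result is at risk from the zero rule.** The primary component uses an absolute increase, so the rule does not enter it. The missing factor of 7 would reach it on a literal reading, but a definition stated per week makes that reading unlikely to be intended.

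The power figures depend on invented count models and are illustrative.

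**What to change.** In SAP 10.2, state that baseline stool frequency and CSBMs are multiplied by 7, so that baseline and follow-up are both per week. This edit is needed whatever is decided about percent change, because the absolute-change test also relies on it.

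In SAP 11.3.2, base inference on the Mann-Whitney test of absolute change in CSBMs per week, which is already planned and matches the scale of the primary component. Drop the percent-change test and the zero-baseline rule. If percent change is still wanted, show it descriptively for subjects with a non-zero baseline and report how many were excluded; that could be a sizeable part of the IBS-C cohort.

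Make both edits before unblinding. The cost is a few lines of SAP wording and the loss of one secondary comparison. Fixing the unit alone would remove the dependence on programming, but would leave zero scored as 1 CSBM per week.

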1 SYNOPSIS

TITLE OF STUDY:

A multicentre Phase 2, randomised, double blind, placebo-controlled, parallel group study to evaluate the safety and efficacy of repeated oral doses of Blautix[™] in adult subjects with irritable bowel syndrome (IBS), subtypes IBS-C and IBS-D

NAME OF SPONSOR: 4D Pharma Plc

Phase 2

Protocol Number: BHT-II-002

Clinical Phase:

Objectives and Endpoints:

The objectives of the study are:

Primary Objective

To assess the efficacy of repeated twice daily doses of Blautix[™] >1x10¹⁰MPN for 8 weeks in adult subjects with either IBS-C or IBS-D

Secondary Objectives

To assess the safety of repeated twice daily doses of Blautix[™] >1x10¹⁰MPN for 8 weeks in adult subjects with either IBS-C or IBS-D

Exploratory Objective

CCI

The endpoints of the study are:

Primary Efficacy Endpoint

The primary efficacy endpoint is whether or not the subject is an overall responder.

A subject is an 'overall responder' if they have reported an improvement in their weekly (Cohort specific) symptoms (abdominal pain intensity and stool frequency or consistency) for \geq 50% of the treatment period (in this case 4 out of 8 weeks).

Secondary Efficacy Endpoints

Subject global assessment of relief

Stool consistency (Cohort C) /Stool frequency (Cohort D)

IBS-QOL

IBS-SSS

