3.2 Endpoints

Primary Efficacy Endpoint

The primary efficacy endpoint is whether the subject is an overall responder.

A subject is an 'overall responder' if they have reported an improvement in their weekly (Cohort specific) symptoms for \geq 50% of the treatment period (4 out of 8 weeks).

	IBS-C	IBS-D	
Primary Endpoint Responder Symptom Definition	Abdominal Pain Intensity Decrease in weekly average of worst abdominal pain in the past 24 hours score of at least 30% compared with baseline	Abdominal Pain Intensity Decrease in weekly average of worst abdominal pain in past 24 hours score of at least 30% compared with baseline	
	And Stool Frequency	and Stool Consistency (BSS)	
	Increase of 1 or more Complete spontaneous bowel movements (CSBM) per week compared with baseline.	Decrease at least 50% in the proportion of days per week with at least one stool that has a consistency of Type 6 or 7 compared with baseline.	

Secondary Efficacy Endpoints

- Subject global assessment of relief
- Stool consistency/frequency
- IBS-QOL
- IBS-SSS
- HADS

Exploratory Endpoints

Safety Endpoints

- Incidence, nature, severity, relatedness, seriousness, expectedness and outcome of adverse events
- Haematology and blood chemistry assessments
- Vital signs

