APPENDIX 6: ROME IV CLASSIFICATION FOR IBS

IBS-C	IBS-D
\Box Abdominal Pain Intensity: weekly average of worst daily (in past 24 hours) abdominal pain score of > 3.0 on a 0 to 10-point scale	\Box Abdominal Pain Intensity: weekly average of worst daily (in past 24 hours) abdominal pain score of > 3.0 on a 0 to 10-point scale
And	And
□ Stool Frequency: more than 25% of bowel movements with a consistency of Type 1 or Type 2 Bristol stool chart and less than 25% of bowel movements with Bristol stool form Type 6 or Type 7. Subject must have fewer than 3 CSBMs within a one-week period (7 days)	□ Stool Consistency: more than 25% of bowel movements with a consistency of Type 6 or Type 7 Bristol stool chart and less than 25% of bowel movements with Bristol stool form Type 1 or Type 2. Subjects must have at least one Type 6 or Type 7 bowel movements on at least four days within a one-week period (7 days).

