#### 10.1.1 Primary Efficacy Endpoint

The primary efficacy endpoint is whether the subject is an overall responder. The definition of an overall responder is IBS subtype specific and consists of two components.

For both IBS subtypes, the first component of overall response is the weekly average of Abdominal Pain Intensity (0-10, 0=none, 10=worst possible pain) over the past 24 hours. Improvement for the week is defined as a decrease of at least 30% compared with baseline.

For the IBS-C subtype, the second component of overall response is the stool frequency per week. Improvement is defined as an increase of 1 or more complete spontaneous bowel movements (CSBMs) per week compared with baseline. The number of bowel movements is recorded once per day in the eCOA device, including zeroes.

For the IBS-D subtype, the second component of overall response is the proportion of days per week with at least one stool with a consistency of Type 6 or 7 on the Bristol Stool Chart. Improvement is defined as a decrease in the proportion of at least 50% compared with the proportion during the 7-day period before baseline used to determine eligibility. Stool consistency is recorded for each bowel movement in the eCOA device, so more than one entry per day may exist. The daily result should be reduced to whether a Type 6 or Type 7 was included on that date.

A subject will be considered a responder only during weeks for which both components indicate improvement. Subjects must have at least 4 evaluable weeks of data as defined in [Section 10.4](#) for each of the instruments used to determine response. Subjects with less than 4 evaluable weeks of assessments available during the treatment period will be considered as non-responders for overall response.

Subjects who have at least 7 evaluable weeks of data and have reported an improvement in their weekly symptoms for  $\geq 50\%$  of the treatment period will be considered overall responders. Subjects who have 4, 5, or 6 evaluable weeks of data must show improvement for  $\geq 60\%$  of the treatment period to be deemed overall responders.

The days for each week will be taken as calendar days from the Day 1 date (randomisation date).

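### SAP 11.3.2 summarises loose-stool days for IBS-C and hard-stool days for IBS-D, the reverse of each subtype's defining stool form, and gives no reason

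*SAP*

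**What the plan says.** SAP 11.3.2 sets out one weekly summary of stool form per subtype. For IBS-C: "The percentage of days each week with at least one stool with a consistency of 6 or 7 will be summarized for IBS-C". For IBS-D: "a consistency of 1 or 2 will be summarized for IBS-D". No test is attached. Under SAP section 6, summary tables are generally shown by treatment group within subtype.

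The subtype table in Protocol 5.1 (repeated in Appendix 6) requires for IBS-C "more than 25% of bowel movements with a consistency of Type 1 or Type 2 Bristol stool chart". For IBS-D it requires the same share of Type 6/7 movements, and adds: "Subjects must have at least one Type 6 or Type 7 bowel movements on at least four days". Each subtype also has a ceiling on the opposite form; for IBS-C this is "less than 25% of bowel movements with Bristol stool form Type 6 or Type 7".

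The second primary component for IBS-D in Protocol 3.2 is a fall of at least 50% "in the proportion of days per week with at least one stool that has a consistency of Type 6 or 7". SAP 10.1.1 agrees: "For the IBS-D subtype, the second component of overall response is the proportion of days per week with at least one stool" of Type 6 or 7. SAP 10.1.2.2, which defines the secondary stool endpoints, derives only weekly stool frequency and a Type 6/7 day proportion, and refers back to 10.1.1 for both. The protocol synopsis lists stool consistency as the secondary endpoint for Cohort C and stool frequency for Cohort D, without saying which stool form the consistency endpoint uses.

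**The concern.** The pairing in 11.3.2 looks transposed. Each subtype is summarised on the stool form that entry keeps uncommon, not on the form that defines its disease. Followed literally, the tables would not show whether hard-stool days change in IBS-C. They would also not show how Type 6/7 days move by week and arm in IBS-D, although those days are half of that cohort's responder definition. If an IBS-D result were driven by only one of pain and stool form, the planned summaries would show the course of pain but not of stool form.

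Timing also matters. SAP section 6 labels anything analysed after the blind is broken as post hoc and exploratory. SAP 10.5 puts the stool consistency tables into the unblinded interim output, so an uncorrected pairing would carry into it.

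**Working it through.** This is a comparison of texts. The plan's one design figure does not enter it. For completeness, that figure reproduces: with 125 per arm, 40% against 55% and one-sided alpha 0.10, exact enumeration of the Yates-corrected test gives 82.5% power, against the stated 80% or more.

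**Step 1. Place every weekly stool-form summary in the visible SAP.**

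| Subtype | Type 1/2 days | Type 6/7 days | Defining form (Protocol 5.1) |
|---|---|---|---|
| IBS-C | none | 11.3.2 | Type 1/2 |
| IBS-D | 11.3.2 | none | Type 6/7 |

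Defining-form cells covered: 0 of 2. Opposite-form cells covered: 2 of 2.

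**Step 2. Look for the missing summaries elsewhere.**

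- IBS-D Type 6/7 days are a baseline characteristic (SAP 9.3) and a logistic covariate (10.3, 11.2). Neither is a post-baseline weekly summary.
- They enter the weekly responder table in 11.2, but only combined with pain.
- Derived weekly values are listed (end of 11.2), not summarised.
- IBS-C Type 1/2 days have no derivation, baseline or summary in the visible text.

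By contrast, pain has weekly summaries and a repeated-measures model in both subtypes (11.2), and CSBM counts have weekly summaries and a Mann-Whitney test (11.3.2). Among the primary components, only IBS-D stool form lacks its own weekly summary by arm.

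**Step 3. Compare 11.3.2 with the derivation.** SAP 10.1.2.2 names no subtype and derives Type 6/7 days only. Its cross-reference leads to 10.1.1, where the measure is the IBS-D component. The IBS-D summary in 11.3.2 uses Type 1/2 days, which section 10 does not derive. In addition, 10.1.2.2 describes days with an increase from baseline in such stools, whereas 10.1.1 counts days with any Type 6/7 stool and treats a decrease in their proportion as improvement.

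**Step 4. Gauge what the IBS-D tables omit.** Entry requires Type 6/7 stools on at least 4 of 7 days: 4/7 = 57.1%. At that minimum, the 50% relative fall needed for improvement takes the proportion to 57.1% × 0.5 = 28.6%. Movement of this kind is what 11.3.2 leaves unsummarised for IBS-D. The form it does summarise in each subtype is held below 25% of movements at entry, so there is little room for it to improve. That ceiling is on movements, not days, so it does not convert directly into a percentage of days.

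**Step 5. Look for a stated reason.** Neither 11.3.2 nor SAP section 13 gives one; section 13 lists only the change to the Efficacy Evaluable set.

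**The case against.** The strongest reply is that the pairing is deliberate. A treatment that overcorrects would produce loose stools in IBS-C and hard stools in IBS-D, and 11.3.2 would detect that. The reference in 10.1.2.2 to an increase in Type 6/7 stools fits such a check in IBS-C, and for IBS-C the form in 11.3.2 is the only one 10.1.2.2 derives. This reading is possible and cannot be excluded. It does not settle the matter: the SAP never states that purpose, 10.1.2.2 ties its measures to the primary components, the IBS-D Type 1/2 measure still has no derivation, and both defining-form summaries are still absent.

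A second reply is that the protocol does not require the missing tables. The synopsis gives Cohort D frequency, not consistency, and does not name the stool form for Cohort C. That stands. The IBS-D part therefore rests on SAP 10.1.2.2 and on the measure being a primary component. The IBS-C part rests on the synopsis endpoint read with the subtype definition.

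Third, the table specifications approved with the SAP (15.3) were not available and may show a different pairing. That limits what can be said about the eventual output. If they do differ, they conflict with 11.3.2, and the text still needs correcting.

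**Conclusion.** The point holds for the visible SAP text. The stool-form summary in 11.3.2 is reversed relative to the subtype definitions, does not match the derivation in 10.1.2.2, and is unexplained. Both defining-form weekly summaries are missing. The wording itself is clear; what would finally be tabulated is less certain, because the table specifications and redacted sections were not available. The consequence is modest: one descriptive secondary summary, with no bearing on the primary test, alpha or sample size, and no effect-size figure attaches to it. It should be corrected because the omitted measures are the subtypes' defining symptoms and the remedy is the same whether the pairing is an error or an undeclared overshoot check.

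**What to change.** Before unblinding, and before the interim tables in SAP 10.5 are produced:

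- In 11.3.2, summarise by week and arm the percentage of days with at least one Type 1/2 stool for IBS-C and at least one Type 6/7 stool for IBS-D.
- If the present pairing was intended as an overshoot check, say so and keep it as a labelled supplementary summary.
- In 10.1.2.2, add a derivation of Type 1/2 days, and reword the Type 6/7 measure to count days with any such stool, as in 10.1.1.
- Add a Type 1/2 baseline to 10.2 only if change from baseline will be shown.
- Align the table specifications.

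The cost is SAP wording, one derived variable and a re-filtered table. The Bristol type of each stool is already in the daily diary, so no new data are needed.
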